3.6.1.1.2. Visit S2 (14 days [± 3 days] after Visit S1)

- Review inclusion/exclusion criteria.
- Perform prior/concomitant medication inquiry.
- Perform adverse event inquiry.
- Perform COVID-19 symptoms inquiry.
- Perform LoAC and CAE inquiry.
- Perform vital signs measurements (includes systolic and diastolic blood pressure, pulse, body temperature, and respiratory rate).
- Perform brief physical examination.
- Distribute e-diary, instruct the patient on how to perform the respective assessments, and perform first assessments.
- Distribute hand-held spirometer.
- Perform reversibility testing (if not completed prior to this visit).
- Perform urine pregnancy testing (women of childbearing potential).
- Repeat testing of peripheral blood eosinophil counts.
- If all inclusion and exclusion criteria, with the exception of the second eosinophil count, are fulfilled within the first 2 weeks, distribute study-provided controller inhalers to standardize the patient's ICS+LABA and commence run-in. This should start at least 2 weeks prior to randomization.

3.6.1.1.3. Visit S3 (14 days [± 3 days] after Visit S2) (if required)

If required, to meet the eosinophil count inclusion criterion, efforts should be made to perform the following assessments and procedures in the order listed:

- Perform prior/concomitant medication inquiry.
- Perform adverse event inquiry.
- Perform COVID-19 symptoms inquiry.
- Perform LoAC and CAE inquiry.
- Review daily e-diary for SABA/quick-relief medication usage and nighttime awakenings, including for adherence.
- Review daily hand-held spirometry, including for adherence.

- Perform vital signs measurements (includes systolic and diastolic blood pressure, pulse, body temperature, and respiratory rate).
- Perform brief physical examination.
- Repeat testing of peripheral blood eosinophil counts.
- Perform urine pregnancy testing (women of childbearing potential).
- Review inclusion/exclusion criteria.
- If the patient has not already started run-in and all inclusion and exclusion criteria are now fulfilled, distribute study-provided controller inhalers to standardize the patient's ICS+LABA and commence run-in. This should start at least 2 weeks prior to randomization.

3.6.1.2. Assessments and Procedures During the Treatment Period

3.6.1.2.1. Assessments and Procedures for the Day of Randomization (Visit 1): Pre-Study Drug Administration; Randomization, and Administration of the Loading Dose

Patients who have been on study-provided controller inhalers for at least 2 weeks and who meet all of the inclusion criteria, none of the exclusion criteria, and all of the randomization criteria proceed to the Day of Randomization (DoR) visit (Visit 1).

Efforts should be made to perform the following procedures in the order listed, at the Day of Randomization visit before IMP administration:

- Review inclusion/exclusion criteria.
- Review randomization criteria.
- Review daily e-diary for SABA/quick-relief medication usage and nighttime awakenings, including for adherence.
- Review daily hand-held spirometry, including for adherence.
- Perform LoAC and CAE inquiry.
- Complete the ACQ-6.
- Check supply and, if required, dispense study-provided controller therapies. Collect returned inhalers.
- Check supply of study-provided SABA. Collect returned inhalers.
- Perform concomitant medication inquiry.
- Perform adverse event inquiry.
- Perform COVID-19 symptoms inquiry.
- Perform ECG in triplicate.
- Perform vital signs measurements (includes systolic and diastolic blood pressure, pulse, body temperature, and respiratory rate).

Clinical Study Protocol with Amendment 02

- Perform full physical examination and document body weight.
- Measure FeNO.
- Perform in-office spirometry (full flow-volume loop).
- Perform urine pregnancy testing (women of childbearing potential).
- Collect samples for clinical laboratory tests (serum chemistry, CBC with differential count, peripheral eosinophil count, urinalysis).
- Collect blood sample for serum TEV-48574 concentration determination (PK assessment) from all patients before IMP administration.
- Collect blood sample for immunogenicity (ADA) assessment.
- Collect blood for [REDACTED] assessment.
- Collect optional blood sample in PaxGene DNA tube for pharmacogenomics analysis.
- Withdraw all controller medications with the exception of ICS/LABA.

Patients who continue to meet all of the inclusion criteria, none of the exclusion criteria, and all of the randomization criteria will be assigned a permanent unique randomization number and a treatment number generated by interactive response technology (IRT). These two newly assigned numbers will be entered into the CRF, and study drug will be dispensed. During the double-blind treatment period, patients will return to the study center every 2 weeks for administration of IMP, assessments and procedures.

The following procedures/assessments will be performed during and after administration of study drug:

- Administer IMP [REDACTED] using the [REDACTED]
- [REDACTED]
- Evaluation of local tolerability at the administration site at 1- and 2-hours post-administration.
- If, during administration or during post-IMP administration observation the patient develops clinical symptoms or signs, vital signs should be collected and a physical exam (brief or full, at the discretion of the investigator) performed. The patient should be assessed for anaphylaxis/hypersensitivity reactions as detailed in Section 7.1.6.

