Reversibility testing may be performed on another day if the patient has not withheld LABA and SABA for the requisite number of hours: reversibility testing should only be attempted after withholding short-acting bronchodilators (ie, inhaled short-acting beta-adrenergic agonists and/or short-acting anticholinergics) for at least 6 hours and long-acting bronchodilators (ie, inhaled long-acting beta-adrenergic agonists and long-acting anticholinergic agents) for at least 12 or 24 hours, according to their labeled dose schedule. Patients may only be asked to hold bronchodilators for reversibility once informed consent has been signed. However, if of their own volition, without being asked, patients have not taken any of the aforementioned bronchodilators for the requisite amount of time prior to the initial screening visit, reversibility may be performed at the initial screening visit.

When the e-diary is dispensed, or when reversibility is performed during screening (whichever comes first), the patient's pre-study quick relief rescue medication will be converted to study-provided albuterol/salbutamol inhalers. The subject's pre-study quick relief rescue medication will be converted to study-provided albuterol/salbutamol inhalers at Visit S1. At Visit S2, once all eligibility criteria (inclusion and exclusion) have been confirmed, with the exception of the second peripheral blood eosinophil count, eligible patients will have their ICS+LABA converted to study-provided ICS+LABA inhalers and commence run-in; this should be completed at least 2 weeks prior to randomization.

All patients will be provided with the strength of inhaled fluticasone propionate plus salmeterol closest to the equivalent of the patient's pre-screening ICS+LABA. This will include fixed-dose combination ICS+LABA and any additional ICS dose. Patients on additional asthma controller medication(s) except those excluded by the eligibility criteria (see Section 4.2) will continue those medications throughout the run-in period and will discontinue them at 4 weeks after randomization (Visit 3).

Treatment Period (16 weeks)

The treatment period begins with randomization and ends with the EOT visit (week 16). After the end of the screening period, patients who meet all of the inclusion criteria (Section 4.1), none of the exclusion criteria (Section 4.2), and all of the randomization criteria (Section 4.3) will be randomized in a 1:1 ratio to the following regimens administered sc every 2 weeks:

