- TEV-48574 [REDACTED]
- Placebo to match TEV-48574

With randomization, patients enter the 16-week treatment period. The patients will receive the IMP loading dose on the day of randomization and the subsequent corresponding IMP maintenance dose every 2 weeks for a total of 8 doses (1 loading dose and 7 maintenance doses).

Patients qualifying for randomization will continue the same background asthma controller regimen as used during run-in without change for the first 4 weeks of the treatment period; this regimen includes study-provided controller inhalers (ICS+LABA and additional ICS), plus any additional controller medications that met the eligibility criteria. After week 4, background asthma controller therapies will be decreased in a structured manner in patients not experiencing LoAC (see Section 6.1.1 for LoAC definition) (the patient will be aware of the dose decreases). The first step is implemented after the first 4 weeks of the treatment period and includes discontinuing LABA and any additional asthma controller medications, with the exception of study-provided additional ICS. The second step will be made 2 weeks later. The second and subsequent steps will consist of decreasing the ICS dose step-wise weekly, by ~50%. For patients on ICS doses greater than the high dose ICS+LABA twice a day, the total ICS dose should also be decreased step-wise weekly, by ~50%. Excluding patients who meet LoAC criteria during the structured withdrawal of background asthma controller therapies, the duration of treatment with IMP only will be approximately 8 or 9 weeks. Since study-provided asthma controller formulations may vary locally, Table 1 shows an example of the step-wise structured withdrawal. Eligibility assessment for structured withdrawal of background asthma controller therapies (between scheduled in-person visits) may be done by phone; if it is suspected that a patient meets the criteria for LoAC, the investigator may ask the patient to attend the site for an unscheduled visit.

Table 1: Examples of Schedule of Withdrawal of Background Asthma Controller Therapies

Time point: Weeks after randomization (visit number)	Action	Dose at start of treatment period	
		Fluticasone/salmeterol 500/50 µg BID	Fluticasone/salmeterol 250/50 µg BID
4 weeks (V3)	Discontinue LABA and other non-ICS asthma controllers*	FP 500 BID	FP 250 BID
6 weeks (V4)	First ICS decrease	500 decreased to 250 BID	250 decreased to 100 BID

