7 weeks (Telephone, V5)	Second ICS decrease	250 decreased to 100 BID	100 BID decreased to 0
8 weeks (V6)	Third ICS decrease	100 BID decreased to 0	0

*Other asthma controllers (eg, LAMA, leukotriene antagonists) will also be discontinued.

Note: Last IMP administration 14 weeks after randomization (visit 9); end-of-treatment visit (EOT) 16 weeks after randomization

BID=twice daily; FP=fluticasone propionate; ICS=inhaled corticosteroids; LABA=long-acting beta-agonists; LAMA= long-acting muscarinic antagonist; V = visit.

Patients will be monitored for worsening of asthma and potential LoAC (and CAE) both at scheduled visits and in between visits via hand-held spirometry and e-diary. Asthma specific alerts will be sent for the following:

- Decrease in morning FEV₁ $\geq 20\%$ from baseline on 2 consecutive days OR decrease in morning PEF $\geq 30\%$ from baseline on 2 consecutive days
- Increase in rescue medication use/SABA of 4 or more puffs over baseline for 2 or more consecutive days OR ≥ 12 puffs in any single day
- Increase of 2 nighttime awakenings due to asthma over baseline on 2 consecutive days

In the event of an alert, the site will follow-up with the patient. An alert does not mean that the patient's medications need to be changed or that study drug should be discontinued, only that the patient should be contacted and evaluated by phone or at an unscheduled visit according to investigator judgment. If, in the investigator's judgment, LoAC is suspected, every effort to have the patient evaluated at an unscheduled visit should be made.

Definitions of LoAC and Clinical Asthma Exacerbation (CAE) are presented in Section 6.1.1 and Section 6.1.2. LoAC events and CAEs will be treated by the investigator according to local standard of care. In the event of a LoAC or CAE, IMP will be discontinued and background asthma controller therapy will be restarted or increased per investigator judgment. Patients who experience LoAC or CAE will remain in the study for assessments. (Note: CAEs are a subset of LoAC events; see Section 6.1.1 and Section 6.1.2 for definitions).

Study procedures and assessments are described in detail Section 3.6.

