Allowed time windows, ±days	-	3	3	3	3	3	3	3	3	3
Inclusion and exclusion criteria	X									
Randomization criteria	X									
LoAC and CAE inquiry ^c	X	X	X	X	X	X	X	X	X	X
Review e-diary for SABA/quick-relief medication usage ^d and nighttime awakenings, including for adherence	X	X	X	X	X	X	X	X	X	X
Review hand-held spirometry, including for adherence	X	X	X	X	X	X	X	X	X	X
ACQ-6	X	X	X	X		X	X	X	X	X
Check supply and, if required, dispense study-provided controller therapies. Collect returned inhalers.	X	X	X	X		X	X	X	X	X
Check supply of study-provided SABA. Collect returned inhalers.	X	X	X	X		X	X	X	X	X

Study period	Treatment Period – Visits 1 – 10									
	V1 DoR	V2	V3	V4	V5 Phone ^a	V6	V7	V8	V9	V10 EOT ^b
Procedures and assessments weeks after random. study day	0 -	2 15	4 29	6 43	7 50	8 57	10 71	12 85	14 99	16 113
Allowed time windows, ±days	-	3	3	3	3	3	3	3	3	3
Concomitant medication inquiry	X	X	X	X	X	X	X	X	X	X
Adverse events inquiry	X	X	X	X	X	X	X	X	X	X
Perform COVID-19 symptoms inquiry ^c	X	X	X	X	X	X	X	X	X	X
ECG ^f	X		X			X		X		X
Vital signs measurement ^g	X	X	X	X		X	X	X	X	X
Full physical examination, including weight ^h	X									X
Brief physical examination		X	X	X		X	X	X	X	
FeNO ⁱ	X	X	X	X		X	X	X	X	X
Background asthma controller therapies withdrawal (other than ICS/LABA)	X									
Background asthma ICS/LABA controller therapies withdrawal evaluation ^j			X	X	X	X	X	X	X	

Study period	Treatment Period – Visits 1 – 10									
	V1 DoR	V2	V3	V4	V5 Phone ^a	V6	V7	V8	V9	V10 EOT ^b
Procedures and assessments weeks after random. study day	0 -	2 15	4 29	6 43	7 50	8 57	10 71	12 85	14 99	16 113
Allowed time windows, ±days	-	3	3	3	3	3	3	3	3	3
In-office spirometry (full flow-volume loop)	X	X	X	X		X	X	X	X	X
Urine pregnancy test ^k	X	X	X	X		X	X	X	X	X
Serum chemistry	X		X			X		X		X
CBC with differential count	X		X			X		X		X
Urinalysis ^l	X									X
Serum drug concentration ^m	X	X	X			X		X		X
ADA ^m	X	X	X			X		X		X
XXXXXXXXXX (exploratory) ^m	X		X			X				X
Pharmacogenomics – Blood in PaxGene DNA tube (optional) ⁿ	X									
IMP administration ^{op}	X	X	X	X		X	X	X	X	
Local tolerability assessment ^q	X	X	X	X		X	X	X	X	

^a For patients who have not withdrawn completely from their background asthma controller therapies due to the patient entering the study on higher background asthma controller therapy doses, further phone visits will be performed between in-person visits after V6, V7 etc. (see Section 3.6.1.2.7)

Clinical Study Protocol with Amendment 02

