3.6.1.2.2. Treatment Visit 2 (Week 2)

At this visit, background asthma controller therapies remain unchanged.

Efforts should be made to perform the following assessments and procedures in the order listed, before administration of study drug:

- Perform concomitant medication inquiry.
- Perform adverse event inquiry.
- Perform COVID-19 symptoms inquiry.

Clinical Study Protocol with Amendment 02

- Review daily e-diary for SABA/quick-relief medication usage and nighttime awakenings, including for adherence.
- Review daily hand-held spirometry, including for adherence.
- Perform LoAC and CAE inquiry.
- Complete the ACQ-6.
- Check supply and, if required, dispense study-provided controller therapies. Collect returned inhalers.
- Check supply of study-provided SABA. Collect returned inhalers.
- Perform vital signs measurements (includes systolic and diastolic blood pressure, pulse, body temperature, and respiratory rate).
- Perform brief physical examination.
- Measure FeNO.
- Perform in-office spirometry (full flow-volume loop).
- Perform urine pregnancy testing (women of childbearing potential).
- Collect blood for serum TEV-48574 concentration determination (PK assessment) from all patients.
- Collect blood sample for immunogenicity (ADA) assessment.

The following procedures/assessments will be performed during and after administration of study drug:

- Administer IMP [REDACTED] using the [REDACTED]
- [REDACTED]
- Evaluation of local tolerability at the administration site at 1- and 2-hours post-administration.
- If, during administration or during post-IMP administration observation the patient develops clinical symptoms or signs, vital signs should be collected and a physical exam (brief or full, at the discretion of the investigator) performed. The patient should be assessed for anaphylaxis/hypersensitivity reactions as detailed in Section 7.1.6.

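### The protocol gives sites two incompatible times for stopping add-on asthma controllers: randomization (Visit 1 list and Table 3) and week 4 (Section 3.1 and Table 1)

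*Protocol*

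**What the plan says.** Two places in the current protocol stop add-on controllers (those other than ICS and LABA) at randomization:

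- Section 3.6.1.2.1, in the list of procedures to be done at Visit 1 before study drug is given: "Withdraw all controller medications with the exception of ICS/LABA".
- Table 3, in the row "Background asthma controller therapies withdrawal (other than ICS/LABA", whose only mark is in the Visit 1 column. ICS/LABA withdrawal has its own row, which starts at Visit 3.

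Section 3.1 and Table 1 stop the same drugs at week 4:

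- Section 3.1, screening and run-in: patients on additional controllers "will continue those medications throughout the run-in period and will discontinue them at 4 weeks after randomization (Visit 3".
- Section 3.1, treatment period: randomized patients "will continue the same background asthma controller regimen as used during run-in without change for the first 4 weeks of the treatment period". That regimen is spelled out as the study inhalers "plus any additional controller medications that met the eligibility criteria".
- Section 3.1, same paragraph: "The first step is implemented after the first 4 weeks of the treatment period and includes discontinuing LABA and any additional asthma controller medications".
- Table 1, footnote to the week 4 (Visit 3) row: "Other asthma controllers (eg, LAMA, leukotriene antagonists) will also be discontinued".

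Other text bears on the point without settling it. Section 3.6.1.2.2 (week 2) says "At this visit, background asthma controller therapies remain unchanged". Section 3.6.1.2.3 starts the structured withdrawal at Visit 3. Section 6.1.1 keeps the regimen stable until the structured withdrawal but names no week. SAP Section 1.7 describes controllers as withdrawn between weeks 4 and 8, although its clause on the first four weeks names only ICS/LABA.

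**The concern.** This is an instruction about what medication a patient takes, and the two versions cannot both be followed. The version that conflicts with the design sits in the visit checklist and the schedule of assessments, the parts a site works from on the day.

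Add-on users are expressly eligible (inclusion criterion h). Those enrolled have an ACQ-6 score of at least 1.5, FEV1 that may be as low as 30% of predicted, and a documented exacerbation in the previous 18 months. Section 3.1 intends them to have 4 weeks of study drug on unchanged background therapy before anything is removed. The Visit 1 item takes that lead-in away for the add-on component, before the first dose.

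There is also a consequence for the trial. The treatment period starts at randomization, so LoAC in weeks 0 to 4 counts toward the primary endpoint, and LoAC ends study drug (Section 6.1.1). An event provoked by an early stop would take the patient off drug before the structured withdrawal under study has begun. If sites differ in which text they follow, background therapy in those weeks differs between sites, and whichever schedule a site follows departs from the other text.

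**Working it through.** The plan states no figure to reproduce on this point. The check is a comparison of the current texts, followed by the size of the timing gap.

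**Side by side**

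| Source | When add-ons stop |
|---|---|
| Protocol 3.6.1.2.1, Visit 1 list | Randomization, before study drug |
| Protocol Table 3, non-ICS/LABA row | Visit 1 only |
| Protocol 3.1, run-in text | Week 4 (Visit 3) |
| Protocol 3.1, treatment period text | Unchanged for 4 weeks, then stopped with LABA |
| Protocol Table 1 and footnote | Week 4 (Visit 3) |
| Protocol 3.6.1.2.3 | Structured withdrawal begins at Visit 3 |
| SAP 1.7 | Withdrawal between weeks 4 and 8 |

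**Can they be reconciled?** One might read the four-week hold as covering ICS+LABA only. Section 3.1 rules this out, because it lists additional controllers within the regimen held unchanged and then stops them together with LABA after week 4. The Table 3 mark cannot be put down to broken table text, because the Visit 1 list gives the same instruction in words. No rule says which protocol section prevails over another. Protocol Section 9 ranks the SAP above the protocol only for descriptions of the analysis.

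**Which time is intended?** Week 4, given the agreement of Section 3.1, Table 1, the Visit 3 text and SAP 1.7. The summary of changes for Amendment 02 suggests the cause: it moved the Section 3.1 stop from randomization to week 4 and gave as its reason that the previous text was incorrect. The Visit 1 item and the Table 3 mark appear to be leftovers of that timing. The finding does not depend on the log, since the conflict lies wholly within current text.

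**Timing gap per affected patient**

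- Visit 1 is day 1 (SAP Table 1; protocol Table 3 shows a dash there). Visit 3 is day 29 (both tables).
- Nominal gap: 29 − 1 = 28 days.
- The Visit 3 window is ±3 days (protocol Table 3), so Visit 3 falls on days 26 to 32. The gap is 26 − 1 = 25 to 32 − 1 = 31 days.

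**Doses before Visit 3**

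- Study drug is given at weeks 0 and 2 before the week 4 visit: 2 doses, of 8 planned (Section 3.1).
- A LoAC event before Visit 3 therefore ends study drug after at most 2 of 8 doses.

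**Number affected**

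The documents give neither the share of patients on add-ons nor how many sites would follow the Visit 1 item. The range is none up to all add-on users.

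**The case against.** The conflict itself is not in dispute. The case for treating it as minor has four parts.

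1. *It is a document correction with no statistical effect.* It is true that no effect on the LoAC comparison is shown. That limits the claim, but it does not answer a contradictory medication instruction for severe patients.

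2. *The early stop is a smaller step than the planned one.* At week 4 the plan removes LABA and add-ons together, and in the Table 1 examples ICS reaches zero by week 8. A patient who stops only the add-on at Visit 1 keeps ICS+LABA for 4 more weeks, with daily spirometry, e-diary alerts and rescue SABA. This stands: the harm is earlier timing without prior study drug, not a harsher withdrawal. The risk is reduced but not removed.

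3. *The documents point to Section 3.1 as governing.* Table 3 footnote j and the texts for Visit 3 and later withdrawal visits refer the structured withdrawal to Section 3.1, and the footnote also cites the pharmacy manual. This lowers the chance of error. However, footnote j is attached to the ICS/LABA row, the Visit 1 item carries no cross-reference, and the pharmacy manual is not available to check.

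4. *The Visit 2 wording is not a further contradiction.* This is fair. A site that stopped add-ons at Visit 1 and changed nothing at Visit 2 would comply with it. The text is neutral, and the conclusion does not need it.

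**Conclusion.** The concern holds: the protocol is wrong as written and must be corrected. Add-on controllers are stopped at randomization in two operative places and at week 4 in Section 3.1 and Table 1, with no reading that fits both. The size is 28 days per affected patient (25 to 31 with the visit window), in an unknown number of patients.

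The priority rests on the conflicting medication instruction alone. Both arms receive it under blinding, so no directional bias is shown, and no effect on the LoAC rate, power or type I error is claimed. ICS+LABA is held for 4 weeks under either reading, so only patients on add-ons are concerned. That week 4 is the intended time is an inference, though a strong one.

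**What to change.** Make week 4 (Visit 3) the single stop time:

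- Delete the add-on withdrawal item from the Visit 1 list in Section 3.6.1.2.1.
- In Table 3, move the mark in the non-ICS/LABA withdrawal row from Visit 1 to Visit 3.
- Check that the pharmacy manual says the same, and notify all sites.
- Before unblinding, tabulate how many patients stopped add-ons before week 4. This would also show whether the error had any reach.

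The cost is two text edits, a site notice to about 75 centers, and one table from concomitant medication data already collected on the CRF (Section 5.10). The sponsor must decide the approval route under Appendix D, which exempts nonsubstantial administrative changes and immediate safety concerns from prior approval. The two administrative letters in Sections 15.2 and 15.4 show that this study has already sent site clarifications without waiting for a full amendment.
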